#### *Safety:*

For the patients treated with sarilumab and concomitant DMARD, a higher incidence of treatment-emergent adverse events (TEAEs), serious adverse events (SAEs), and TEAEs leading to discontinuation were observed in the sarilumab treatment groups compared to the placebo group. The incidence of TEAEs leading to death was similar in sarilumab and placebo groups.

In the placebo-controlled population, compared to the placebo group, higher incidences of TEAEs, SAEs, and TEAEs leading to discontinuation were observed in sarilumab 200 mg q2w or 150 mg q2w + DMARD treatment groups relative to the placebo + DMARD group. These differences were generally attributable to higher rates of the AESIs associated with IL-6 blockade, specifically infections and laboratory abnormalities (including decrease in absolute neutrophil count (ANC) and platelet count, increase in transaminase and lipids) in the sarilumab + DMARD groups.

The observations with regards to adverse event (AE) and laboratory parameters with long-term administration were consistent with what was observed in the placebo-controlled population, and no safety findings were identified as attributable to long-term administration.

#### *Other diseases:*

Sarilumab was studied in ankylosing spondylitis (AS) patients in the DRI11073 study. Patients who completed the DRI11073 study had the possibility of enrolling in the LTS11298 long-term safety study if appropriate. The DRI11073 study failed to demonstrate clinical efficacy and the clinical development in this indication has been terminated. Consequently the LTS11298 study was prematurely discontinued. Overall, the safety observations from these studies conducted in patients with AS were consistent with what has been observed in patients with RA.

Sarilumab was also evaluated in a randomized double-blind Phase 2 study of patients with noninfectious uveitis (NIU) (ACT13480/SARIL-NIU-SATURN). Although the primary efficacy endpoint of a 2 step reduction in vitreous haze (VH) or reduction in steroid dose was not met, significant improvements were observed for key secondary endpoints such as change from baseline in adjudicated VH at Week 16, change from baseline in best-corrected visual acuity (BCVA) at Week 16, and change from baseline central retinal thickness (CRT) at Week 16. Furthermore, changes in adjudicated VH, BCVA, and CRT were maintained at Week 52. No new safety signals have been detected with sarilumab use in NIU compared with other indications. The AEs and laboratory changes were consistent with results observed in studies with sarilumab in RA patients and with IL-6 inhibition.

The FDA has approved sarilumab for the treatment of rheumatoid arthritis. It is not FDA approved for the treatment of sarcoidosis, however this clinical investigation is exempt from an IND as it meets the following requirements:

- Sarilumab is lawfully marketed in the United States
- The investigation is not intended to be reported to the FDA as a well-controlled study in support of a new indication and there is no intent to use it to support any other significant change in the labeling of the drug
- The investigation is not intended to support a significant change in the advertising for the drug
- The investigation does not involve a route of administration, dose, patient population, or other factor that significantly increases the risk associated with the drug
- The investigation is conducted in compliance with the requirements for review by the Stanford IRB and with the requirements for informed consent
- The investigation is not intended to promote or commercialize the drug

### **2.3 Rationale**

Sarcoidosis is a chronic illness, requiring long-term immunosuppression. There are no established guidelines for the treatment of sarcoidosis, but the mainstay therapy is glucocorticoids. It is well established that prolonged use of glucocorticoids has a number of harmful effects, including glucose intolerance, osteoporosis, weight gain, hypertension, hyperlipidemia, infection, insomnia, cataracts, gastrointestinal perforation, and mood changes [3-5]. Thus, it is essential for patients who do not respond to glucocorticoids to be treated with additional agents in hopes of minimizing exposure to steroids. Typically, a disease modifying anti-rheumatic drug (DMARD), such as methotrexate or azathioprine, is added to prednisone. When this fails, and for severe manifestations, more potent drugs are used such as cyclophosphamide or a biologic drug such as a TNF-inhibitor. Despite these therapies, many patients have ongoing sarcoidosis symptoms and organ injury.

Interleukin-6 (IL-6) is elevated in the blood and bronchoalveolar (BAL) fluid of patients with sarcoidosis [6, 7]. This inflammatory cytokine leads to B cell differentiation into antibody-secreting cells. Patients with sarcoidosis have elevated blood levels of immunoglobulins, consistent with B cell hyperactivation [7]. In addition, these activated B cells can serve as highly affinity-matured antigen presenting cells for T cells. IL-6 also stimulates T cells directly and specifically induces Th17 T cell development. Th17 cells are elevated in sarcoidosis and likely contribute to disease pathogenesis through secretion of IL-17 and interferon-gamma (IFN- $\gamma$ ) [8-10]. IL-6 additionally inhibits Treg differentiation, thereby decreasing the population of cells responsible for restraining the effector T cell response [11].

Sarilumab binds the IL-6 receptor and prevents its activity. It has been studied extensively in rheumatoid arthritis (RA), and has been shown to improve disease activity, radiographic findings, and markers of inflammation [12-15]. Given sarilumab's efficacy and favorable safety profile, it is now FDA-approved for the treatment of RA. Sarilumab has never been tested in sarcoidosis patients, and we believe it will have similar efficacy when given to this patient population. There are limited options in the management of sarcoidosis, and determining whether novel approaches such as sarilumab are useful for improving patients' quality of life and for decreasing morbidity and mortality is critical.

## **2.4 Study Design**

The primary purpose of this study is to evaluate sarilumab in the treatment of sarcoidosis. The first period of this trial, Period 1, is single-arm and open-label, in which all patients will receive sarilumab. The second period, Period 2, is a two-arm, randomized withdrawal study in which half of the patients will receive sarilumab and half will receive matching placebo. Period 2 will be double blind. The primary outcome of the study is designed to evaluate efficacy of sarilumab in the treatment of sarcoidosis.

## **2.5 Correlative Studies Background**

A plasma sample (5 ml) will be collected for future biomarker analysis at Baseline, Week 16, and Week 28. This will be used to study cytokines including IL-6 levels. Peripheral blood mononuclear cells will also be collected at Baseline, Week 16, and Week 28. These will be used to characterize the immune response before and after treatment.

# **3. PARTICIPANT SELECTION AND ENROLLMENT PROCEDURES**

## **3.1 Inclusion Criteria**

- (1.) Men and women of all races and ethnicities age 18 to 80.
- (2.) Biopsy proven non-caseating granulomas consistent with sarcoidosis, with negative infectious studies including AFB and fungal stains, and with compatible clinical and/or radiographic manifestations of sarcoidosis.
- (3.) Involvement of the lungs (stage II or III pulmonary sarcoidosis), lymph nodes, liver, kidneys, spleen, bone, soft tissues, skin, and/or eyes.
- (4.) At least one active manifestation, defined by the need for ongoing glucocorticoid treatment to control a sign or symptom of sarcoidosis, which requires treatment with prednisone (or equivalent

corticosteroid)  $\geq$  10 mg and  $\leq$  60 mg daily (i.e. glucocorticoid dependence), with stable dosing for  $\geq$  28 days prior to baseline. If patients are taking a glucocorticoid other than prednisone, they will be changed to prednisone at the equivalent dose and take this daily for  $\geq$  14 days prior to baseline.

(5.) DMARDs including methotrexate, leflunomide, azathioprine, mycophenolate mofetil, and/or anti-malarials (i.e. hydroxychloroquine) will be permitted, but the regimen must be stable for  $\geq$  28 days prior to baseline and remain stable during follow-up.

(6.) Ability to understand and the willingness to sign a written informed consent document.

### **3.2 Exclusion Criteria**

- (1.) Patients  $<$  18 years of age or  $>$  80 years of age.
- (2.) Stage IV pulmonary sarcoidosis.
- (3.) Central nervous system sarcoidosis.
- (4.) Cardiac sarcoidosis.
- (5.) Prior treatment with an anti-IL-6 therapy.
- (6.) Treatment with a biologic agent including rituximab, belimumab, TNF inhibitors, abatacept, or IL-17 inhibitors administered within 28 days prior to baseline (6 months for rituximab).
- (7.) Treatment with cyclophosphamide within 3 months prior to baseline.
- (8.) Treatment with prednisone  $<$  10 mg or  $>$  60 mg daily.
- (9.) Known hypersensitivity or allergy to the study drug.
- (10.) History of, or current, inflammatory or autoimmune disease other than sarcoidosis which would present a safety issue or confound interpretation of the data.
- (11.) Prior or current history of other significant concomitant illness that, according to the investigator's judgment, would adversely affect the patient's participation in the study. These include, but are not limited to, cardiovascular (including stage III or IV cardiac failure according to the New York Heart Association classification), neurological (including demyelinating disease), active infectious diseases, or history of diverticulitis or gastrointestinal perforation.
- (12.) Patients currently pregnant or breast-feeding.
- (13.) Women of childbearing potential (WOCBP) who are unwilling to utilize adequate contraception and unwilling to not become pregnant during the full course of the study (must be willing to be tested for pregnancy). Adequate contraceptive measures include oral contraceptives (continuous use, as per prescription, for 2 or more cycles prior to screening), intrauterine devices, contraceptive sponges, condoms or diaphragms plus foam, or jelly, or surgical procedures such as bilateral tubal ligation or vasectomy in partner.
- (14.) Administration of a live/attenuated vaccine within 30 days.
- (15.) Evidence of active tuberculosis, HIV, or hepatitis B or C infection.
- (16.) History of cancer other than non-melanoma skin cancer.
- (17.) Patients with any of the following laboratory abnormalities at the screening visit: hemoglobin  $<$  8.5 g/dL, white blood cells  $<$  3000/mm^3, neutrophils  $<$  2000/mm^3, platelet count  $<$  150,000 cells/mm^3, aspartate aminotransferase (AST) or ALT  $>$  1.5 x ULN, and/or bilirubin (total) above the upper limit of normal (unless Gilbert's disease has been determined by genetic testing and documented).
- (18.) Presence of severe uncontrolled hypercholesterolemia ( $>$  350 mg/dL, 9.1 mmol/L) or hypertriglyceridemia ( $>$  500 mg/dL, 5.6 mmol/L) at screening or baseline.
- (19.) Patients with calculated creatinine clearance  $<$  30 mL/minute (using Cockcroft-Gault formula).
- (20.) History of alcohol or drug abuse within 5 years prior to the screening visit.
- (21.) Participation in any clinical research study evaluating another investigational drug or therapy

within 5 half-lives or 60 days of first investigational medicinal product (IMP) administration, whichever is longer.

(22.) Any patient who has had surgery within 4 weeks prior to the screening visit or with planned surgery during the course of the study.

### **3.3 Informed Consent Process**

All participants will be provided a consent form describing the study with sufficient information for participants to make an informed decision regarding their participation. Participants must sign the IRB approved informed consent prior to participation in any study specific procedure. The participant will receive a copy of the signed and dated consent document. The original signed copy of the consent document will be retained in the medical record or research file.

### **3.4 Randomization Procedures**

In Period 2 of the study, patients will be randomized to sarilumab or matching placebo. This will be done by our administrative assistant [name] using a computer-generated random number. An odd number will be assigned to sarilumab and an even number will be assigned to placebo. Only [name] will be aware of the assignment and she will communicate this directly to the Investigational Pharmacy. The investigators and patients will remain blinded. The codebook with the patient assignments will be stored by [name] in a secure, locked file cabinet.

### **3.5 Study Timeline**

#### **Primary Completion:**

The study will reach primary completion 15 months from the time the study opens to accrual.

#### **Study Completion:**

The study will reach study completion 24 months from the time the study opens to accrual.

## **4. TREATMENT PLAN**

At Screening, vital signs will be obtained, a physical examination performed, and complete medical history obtained. **Routine clinical laboratory tests** (including a chemistry panel, complete blood count, urinalysis, spot urine protein and creatinine, C-reactive protein (CRP), erythrocyte sedimentation rate (ESR), urine pregnancy test), **sarcoidosis-related laboratory tests** (including angiotensin converting enzyme (ACE), total immunoglobulins (IgG), urine calcium, 25-hydroxy vitamin D, and **safety laboratory tests** (including serum pregnancy test for females, HIV test, hepatitis B test, hepatitis C test, and quantiferon test for tuberculosis) will be performed. An electrocardiogram and chest x-ray will also be obtained. At Baseline and Week 16, routine clinical laboratory tests and sarcoidosis-related laboratory tests will be repeated, and in addition the following tests will be performed at Baseline (and only repeated at Week 16 if abnormal at Baseline): pulmonary function tests, chest computed tomography, creatinine kinase (CK), aldolase, and lactate dehydrogenase (LDH). At Week 28, routine clinical laboratory tests and sarcoidosis-related laboratory tests will be repeated. At visits 3-11, vital signs, a physical examination, a medical history, and routine clinical laboratory tests will be obtained, urine pregnancy test for WOCBP. At Baseline, Week 16, and Week 28 the ePOST, global patient VAS, global physician VAS, HAQ, and FACIT-F will be assessed. Also at Baseline, Week 16, and Week 28, eight green

top tubes will be collected and processed for plasma and peripheral blood mononuclear cells, which will be stored at -80°C for future research.

During Period 1 (Baseline through Week 16), all subjects will receive 200mg of sarilumab subcutaneously every two weeks. During Period 2 (Week 16 through Week 28), half of the subjects who responded in Period 1 will receive 200mg of sarilumab subcutaneously every two weeks and half of the subjects will receive matching placebo in a double-blinded fashion.

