## 9. STUDY CALENDAR

	Screen Day -35 to 0	Baseline Day 1	Week 2	Week 4	Week 8	Week 12	Week 16	Week 18	Week 20	Week 24	Week 28	Week 34	ET	Unscheduled visit
Written IC	X													
Randomization		X												
Medical history	X													
Vital signs	X	X	X	X	X	X	X	X	X	X	X	X	X	X
Complete PE	X											X	X	
Limited PE		X	X	X	X	X	X	X	X	X	X			X
ePOST		X					X				X			X
Global VAS patient		X					X				X			X
Global VAS physician		X					X				X			X
FACIT-F and HAQ		X					X				X			X
Routine clinical labs:														
Chemistry panel	X	X	X	X	X	X	X	X	X	X	X	X	X	X
CBC w/diff	X	X	X	X	X	X	X	X	X	X	X	X	X	X
Urinalysis, urine P/C	X	X	X	X	X	X	X	X	X	X	X	X	X	X
ESR, CRP	X	X	X	X	X	X	X	X	X	X	X	X	X	X
Urine pregnancy		X	X	X	X	X	X	X	X	X	X	X	X	X
Sarcoidosis labs:														
ACE level	X	X					X				X			X
Immunoglobulins	X	X					X				X			X
Urine calcium	X	X					X				X			X
25-hydroxy vit D	X	X					X				X			X
Safety labs:														
Serum pregnancy	X													
HIV-1/2 serology	X													
Hepatitis B serology	X													
Hepatitis C serology	X													
QuantiFERON TB	X													
Screening tests:														
EKG	X													
Chest x-ray	X													
Sarcoid-specific tests:														
Pulm Function Test		X					X							
CT chest		X					X							
CK, aldolase, LDH		X					X							
Research labs:														
Plasma		X					X				X			
PBMCs		X					X				X			
Review AEs and meds	X	X	X	X	X	X	X	X	X	X	X	X	X	X
Study drug dispensing		X		X	X	X	X		X	X	X			
Drug accountability			X	X	X	X	X	X	X	X	X			X

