## 10. MEASUREMENTS

### 10.1 Primary and Secondary Outcome measures

*Primary endpoint:* The primary endpoint is the flare-free survival of sarilumab-treated patients compared to placebo-treated controls in the double-blind randomized withdrawal period (Period 2) from Week 16 to Week 28. Patients will be considered to have flared if they receive rescue medication including increased glucocorticoids, or if they discontinue the study treatment in order to start a different therapy.

*Secondary endpoints:* The following secondary endpoints will all be assessed at Week 16 and Week 28 compared to baseline as a paired analysis: the change in the extrapulmonary physician organ severity tool (ePOST) score (17 organs rated 0-6, for a total score range of 0-102) [16], the change in global score of sarcoidosis using a visual analogue scale (VAS) by both the patient and physician (distance in mm measured on a 10 cm line), the change in FACIT-F score (fatigue scale ranging from 0-52 with higher score meaning less fatigue), the change in the Health Assessment Questionnaire (HAQ), the change in prednisone dose, the change in serum angiotensin converting enzyme (ACE), serum immunoglobulin G (IgG) levels, serum calcium, urine calcium, and serum 25-hydroxy vitamin D (25-OH-vit D), the change in pulmonary function tests (FVC, FEV1, and DLCO), the change in ALT, AST, and alkaline phosphatase, the change in serum creatinine and urine protein levels, the change in the Sarcoidosis Activity and Severity Index for cutaneous sarcoidosis (7 parameters scored 0-4 for a total score range of 0-28) [17], the change in CK, aldolase, and LDH, and the change in size of sarcoidosis lesions (i.e. enlarged lymph nodes, hepatic nodules, pulmonary nodules) by CT imaging. For patients with known or suspected ocular involvement, the secondary endpoint of change in ophthalmology global assessment of ocular sarcoidosis using a visual analogue scale (VAS) (distance in mm measured on a 10 cm line) [18] will be assessed, as well as the change in any one or more of the following parameters: best corrected visual acuity (BCVA), slit lamp examination (including grading of anterior chamber cells), tonometry, dilated indirect ophthalmoscopy (including grading of vitreous cells and haze), optical coherence tomography (OCT) and OCT angiography, color fundus photography, and fluorescein angiography.

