# **12. STATISTICAL CONSIDERATIONS**

## **12.1 Statistical Design**

Patient characteristics including demographics, medical history, and concomitant medications will be summarized. The summaries will be done using descriptive statistics, eg, mean, standard deviation, median, minimum and maximum for quantitative values and counts and percents for qualitative variables.

The primary efficacy analysis of flare-free survival in Period 2 from Week 16 to Week 28 will use the intention-to-treat (ITT) population and will be assessed with Kaplan-Meier methods. **Patients will be considered to have flared in Period 2 if they receive rescue medication including increased glucocorticoids, or if they discontinue the study treatment in order to start a different immunosuppressive therapy.**

For Period 1, secondary endpoint variables will be treated as continuous and the values at Week 16 will be compared to Baseline values using Wilcoxon signed-rank tests. The number of patients in glucocorticoid-free remission at week 16 will be reported. Patients will be considered non-responders in Period 1 if they are unable to complete the glucocorticoid taper, receive rescue medication including increased glucocorticoids, or discontinue the study treatment in order to start a different therapy. For Period 1 secondary efficacy endpoints, non-responders will be included in the analysis only if their prednisone dose is equal to or less than the starting dose and stable for the 4 weeks preceding Week 16. The rationale for this is that patients who flare despite sarilumab therapy might be given high doses of steroids, thus improving their endpoints and falsely attributing the success to sarilumab. As a sensitivity analysis, we will also assess the secondary outcomes using the baseline observation carried forward (BOCF) for those patients deemed non-responders.

For Period 2, time to first flare will be compared using a 2-sided log-rank test. The proportion of patients in glucocorticoid-free remission at week 28 in sarilumab-treated patients compared to placebo controls will be analyzed using a Fisher's exact test. The remaining secondary endpoint variables will be treated as continuous and the values at Week 28 will be compared to Week 16 and to Baseline values using Wilcoxon signed-rank tests. We will not perform any corrections for multiple hypothesis testing due to the exploratory nature of this pilot study which solely aims to generate areas of potential future investigation.

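### Section 4 repeats PFTs, CT, CK, aldolase and LDH at Week 16 only if abnormal at Baseline, contradicting Sections 9 and 10.1; if followed, the change in these secondary endpoints is tilted toward improvement

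*Combined protocol and SAP*

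**What the plan says.** Three parts of the protocol describe the same tests differently.

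- Section 4 performs the tests at Baseline under this rule: "and only repeated at Week 16 if abnormal at Baseline): pulmonary function tests, chest computed tomography, creatinine kinase (CK), aldolase, and lactate dehydrogenase (LDH". It does not say what counts as abnormal, or whether the rule applies test by test. It schedules none of these tests at Week 28.
- Section 9 (calendar) has rows for "Pulm Function Test", chest CT and "CK, aldolase, LDH". Each is marked at Baseline and Week 16 with no condition shown, and none is marked at Week 28.
- Section 10.1 states: "The following secondary endpoints will all be assessed at Week 16 and Week 28 compared to baseline as a paired analysis". The list includes "the change in pulmonary function tests (FVC, FEV1, and DLCO") and "the change in CK, aldolase, and LDH, and the change in size of sarcoidosis lesions" on CT. It is not limited to patients who were abnormal at Baseline.

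For Period 1, Section 12.1 says that "the values at Week 16 will be compared to Baseline values using Wilcoxon signed-rank tests". It includes a non-responder only if prednisone is no higher than the starting dose and has been stable for the four weeks before Week 16. A baseline-carried-forward sensitivity analysis covers non-responders. There is no rule for a responder who has no Week 16 value because the Baseline test was normal.

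**The concern.** Under Section 4, the Baseline reading decides who is measured again, and that same reading is then subtracted from the Week 16 value. Patients chosen because a reading was poor will on average read somewhat better next time, even on an inert drug. Section 2.4 makes Period 1 single-arm, so no comparison group removes this.

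There is also a blind spot. Section 3.1 requires "At least one active manifestation, defined by the need for ongoing glucocorticoid treatment to control a sign or symptom of sarcoidosis", so a test may be normal at Baseline because prednisone is working. The taper runs from Week 4 to Week 16. If such a patient's result on one of these tests deteriorates, no Week 16 value exists to show it.

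At stake is the secondary objective in Section 1.2 of showing that sarilumab reduces disease manifestation-specific metrics. Lung function matters most here: Section 2.1 puts lung involvement at about 90%, and ePOST is an extrapulmonary tool.

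**Working it through.** The plan gives no figure on this point to reproduce.

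**Inputs from the documents.** 15 patients in Period 1 (Section 12.3); no control arm (Section 2.4); signed-rank test of Week 16 against Baseline (Section 12.1); repeat only if abnormal (Section 4).

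**Assumptions, not in the documents.** Baseline and Week 16 values are jointly normal with the same mean and SD (no true change) and correlation r of 0.7 to 0.9. Abnormal means the worst share p of patients, with p from 30% to 90%.

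**Step 1: expected shift.** In the re-tested patients, the apparent mean improvement in Baseline SDs is (1 − r) × φ(c)/p, where c is the normal quantile of 1 − p.

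- p = 0.3: φ(c)/p = 0.3477/0.3 = 1.159; times 0.1, 0.2, 0.3 gives 0.12, 0.23, 0.35.
- p = 0.5: 0.3989/0.5 = 0.798; gives 0.08, 0.16, 0.24.
- p = 0.7: 0.3477/0.7 = 0.497; gives 0.05, 0.10, 0.15.
- p = 0.9: 0.1755/0.9 = 0.195; gives 0.02, 0.04, 0.06.

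The omitted patients would move the other way by (1 − r) × φ(c)/(1 − p), so the average over all 15 is zero. The shift comes entirely from the selection.

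**Step 2: effect on the test.** I simulated 15 patients, kept those abnormal at Baseline and applied the exact two-sided signed-rank test at 0.05 (40,000 trials per scenario, no true change).

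| Share abnormal | Expected n of 15 | Shift (SD), r = 0.9 to 0.7 | Two-sided rejection | Rejections that are improvements |
|---|---|---|---|---|
| 30% | 4.5 | 0.12–0.35 | 1.8–3.7% | 94–99% |
| 50% | 7.5 | 0.08–0.24 | 5.2–8.7% | 88–97% |
| 70% | 10.5 | 0.05–0.15 | 5.5–7.9% | 82–94% |
| 90% | 13.5 | 0.02–0.06 | 4.9–5.6% | 65–77% |

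If all 15 are re-tested, the exact size is 4.8%, so a false improvement occurs in 2.4% of trials. Under the rule, with 50% abnormal and r = 0.7, it occurs in 8.7% × 0.975 = about 8.5%.

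At 30% abnormal the low rejection rate is no reassurance. The smallest two-sided p-value is 2/2⁵ = 0.0625 at n = 5, so the test cannot reject with five or fewer patients, and that happens in 72% of trials (binomial, 15 patients, 0.3). The estimate is still shifted.

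**Step 3: unrecorded worsening.** As an illustration, suppose 5 of 15 patients are normal on a test and each has a 10% to 30% chance of new worsening on it. The chance of at least one unrecorded case is 1 − 0.9⁵ = 41% to 1 − 0.7⁵ = 83%.

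**The case against.** The strongest reply is that the bias may never arise. The calendar shows the tests at Week 16 without a condition, and Section 10.1 says all these endpoints are assessed. If those sections govern, nobody is selected. This stands as far as it goes: the certain defect is the contradiction, and the bias is conditional on following Section 4. But Section 4 contains the only explicit rule, and nothing says that the calendar overrides it.

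Three stronger readings should be resisted.

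- A reader might fix the number of abnormal patients at 8 and infer rejection rates of 6% to 18%. The top of that range pairs 30% abnormal with n = 8. With 15 patients, 8 or more abnormal at that share has a probability of only 5%.
- A reader might infer that the plan cannot show organ worsening during the taper. The gap covers only these tests in patients normal at Baseline. Worsening of an already abnormal test is recorded. Every patient has examination, routine laboratory tests and adverse event review, and has ePOST, global VAS, HAQ and FACIT-F at Week 16. Worsening that leads to rescue or an incomplete taper counts as non-response.
- A reader might infer that omitted patients could only stay the same or worsen. These are mostly continuous measures, and a value in the normal range can move either way.

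It is also fair to say that these are exploratory, uncorrected secondary endpoints, and that an open-label period without a control cannot attribute change to sarilumab even if everyone is re-tested. That limits the consequence. It does not justify adding a bias of known direction that can be avoided cheaply.

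**Conclusion.** The concern holds in this limited form. Sections 4, 9 and 10.1 disagree, and abnormal is undefined. If Section 4 is followed, the Week 16 change in FVC, FEV1, DLCO, CT lesion size, CK, aldolase and LDH is shifted toward improvement, and new worsening on these tests in Baseline-normal patients is lost.

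The direction follows from the rule itself whenever repeat readings are imperfectly correlated. The size rests on assumed correlations and abnormal shares. It is modest for tests abnormal in about half of patients or fewer, and close to negligible for a reliable test abnormal in nearly all. CT may be such a test, given the stated lung involvement. The randomized primary endpoint is not affected.

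**What to change.** - **PFTs, CK, aldolase, LDH.** Delete the condition in Section 4, so that every patient is tested at Week 16 as the calendar shows. Analyse all patients with a Week 16 value, subject to the Section 12.1 rule for non-responders.
- **CT.** Section 4.1 puts the radiation from a chest CT at roughly 70 chest x-rays, which is a reason to keep the repeat conditional. If it stays so, define abnormal, add the condition to the calendar, report the number scanned twice, and state that the result describes lesion change in that subset only and cannot show new disease.
- **Week 28.** Reconcile Section 10.1, which promises these endpoints at Week 28, with Sections 4 and 9, which schedule no such tests then. Either schedule them or limit these endpoints to Week 16.

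The cost is a few edited sentences plus some extra PFTs and blood tests in at most 15 patients, at a visit where the calendar already lists them and blood is already drawn. The change must precede the Week 16 visits, because a missed Week 16 test cannot be done later.
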